3.13. Data analysis

Categorical variables will be presented as absolute and relative frequencies.

Quantitative variables will be presented as mean and standard deviation or as median and interquartile range when appropriate. We will use the Kolmogorov-Smirnov test to assess the distribution pattern of continuous numerical variables.

Comparisons between general anesthesia + block and block + sedation will be performed, as well as comparisons between standard and continuous monitoring. Proportions will be compared using the Chi-square test or Fisher's exact test, if the assumptions for using the Chi-square are violated. Quantitative variables will be compared using the Mann-Whitney test or irregularly distributed Anova when appropriate.

Variables with repeated measurements will be analyzed by linear general multiple model (GLM) with Bonferroni correction for P values.

The association between explanatory variables and response will be evaluated using logistic regression models. Variables selected in the bivariate analyzes ($p<0.05$) and those considered clinically relevant will be submitted to multiple logistic regression analyses. Variables with substantial collinearity will be excluded. The result of logistic regression analyzes will be expressed as odds ratios and respective 95% confidence intervals.

All significance probabilities (P values) presented will be two-tailed. P values will be considered statistically significant when less than 0.05. *The Statistical Package for Social Sciences* software version 26.0 (SPSS Inc.®; Chicago, IL, USA) will be used to perform the analyses.

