3.6. Calculation of the sample size

Based on the sample calculation, the study by Soeding PF et al, 2011 (22) , which observed a drop in MAP under general anesthesia of approximately 30%, the study by Vincent S et al, 2005 (24) , which observed a decrease in MAP under sedation of 5.6%, and the study by Meidert et al 2017 (25) , which observed a decrease in SBP of 18 mmHg and 12 mmHg of MAP in the group with intermittent monitoring in relation to the group with continuous monitoring. Based on these data, a difference in mean total MAP between groups of 12 mmHg was used and therefore, considering the study power of 80% and alpha error of 0.025 by Bonferroni correction due to be divided into 4 groups, a total sample of 92 patients will be need, with standard deviation of the group with continuous monitoring of cardiac output of 10 mmHg and in the group standard monitoring of 15 mmHg. However, estimating that we may have losses, the final sample will reach 100 patients, so there will be 25 patients in each of the 04 groups.

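### The 12 mmHg difference in mean MAP that sizes the trial is not tied to one analysis, and no baseline-adjusted estimate with a confidence interval is planned

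*Combined protocol and SAP*

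**What the plan says.** Section 3.6 states the quantity on which the trial is sized: "a difference in mean total MAP between groups of 12 mmHg was used". The other inputs are 80% power, an "alpha error of 0.025 by Bonferroni correction due to be divided into 4 groups", a "standard deviation of the group with continuous monitoring of cardiac output of 10 mmHg" and, "in the group standard monitoring of 15 mmHg". The result is that "a total sample of 92 patients will be need", raised to 100 (25 per group) for losses.

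Section 3.13 has three sentences that could govern the analysis of MAP:
- A distribution check: "We will use the Kolmogorov-Smirnov test to assess the distribution pattern of continuous numerical variables".
- A test for quantitative variables: "Quantitative variables will be compared using the Mann-Whitney test or irregularly distributed Anova when appropriate".
- A general linear model, with Bonferroni-corrected P values, for variables measured repeatedly.

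Under 3.10, MAP, heart rate and cerebral saturation are recorded every 5 minutes during surgery and recovery. Section 3.13 attaches confidence intervals only to odds ratios. Baseline values appear only in the 3.7 definitions of hypotension and of reduced cerebral saturation, each of which includes a 20% fall from the starting value.

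**The concern.** The sample size rests on one estimand, a difference in means in mmHg, but the plan does not commit to an analysis that must deliver it. If MAP is reduced to one value per patient, the method is a rank test or ANOVA. On the natural reading, that choice is made after seeing the Kolmogorov-Smirnov result. As printed, the sentence also pairs ANOVA with irregular data, which is the reverse of usual practice. If the 5-minute series is analysed, the method is the general linear model, but no time window, contrast, baseline term or effect estimate is named for it.

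Three candidate analyses without a rule for choosing leave the main result open to a choice made after the data are seen. A P value from the rank route would not answer the question the trial was sized for. In addition, starting MAP must be collected for the 20% definition, yet no comparison is said to use it to reduce variance.

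**Working it through.** **1. Reproduce the plan's figure.** Inputs from 3.6: difference 12 mmHg, SDs 10 and 15, alpha 0.025, power 80%. Section 3.13 makes tests two-sided.

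- Root-mean-square SD = √((10² + 15²)/2) = √162.5 = 12.75.
- Standard error at 23 per group = √(10²/23 + 15²/23) = √14.13 = 3.76, so the standardised difference is 12/3.76 = 3.19.
- Two-sample t-test power (noncentral t): 78.4% at 22 per group and 80.5% at 23. The Welch version gives 78.0% and 80.1%.
- 23 × 4 = 92, the stated total.

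The stated size is therefore that of an unadjusted comparison of means between two single groups of 23. It is not a rank-test or repeated-measures calculation.

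**2. Effect of the choice of test if MAP is normal.** Simulation with the plan's SDs, 12 mmHg and alpha 0.025:

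| Comparison | t or Welch | Mann-Whitney | Pre-test, then t or Mann-Whitney |
|---|---|---|---|
| 23 v 23 | 80.5% | 76.7% | 80.2% |
| 46 v 46, Welch (separate run) | 98.5% | 98.1% | not tabulated |

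At 23 v 23 the two-stage rule (Lilliefors-corrected Kolmogorov-Smirnov test) had type I error 2.2% against a nominal 2.5%. The 46 v 46 row matters because 3.13 compares technique and monitoring overall, which pools two groups on each side.

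**3. Effect if the variable is skewed.** This rests on an assumed log-normal shape (sigma 0.5), which the documents neither state nor exclude. The Lilliefors-corrected check sent about 62% of 23 v 23 comparisons and 89% of 46 v 46 comparisons to Mann-Whitney. With equal means and SDs of 10 and 15, the two-stage rule rejected in 4.0% and 6.9% of runs at nominal 2.5%, against about 2.6% for the t-test. The switch changes the hypothesis from equal means to one about ranks. Without the Lilliefors correction the check fired in only about 4% and 18% of these runs. The plan does not say which form is meant.

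**4. Effect of using baseline MAP.** The documents give no correlation r between baseline and intraoperative MAP, so r = 0.3 to 0.6 is an assumption. Residual SD = SD × √(1 − r²). At 23 v 23, 12 mmHg and alpha 0.025:

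| r | √(1 − r²) | Power by formula | Simulated power, linear model with HC3 robust errors |
|---|---|---|---|
| none | 1 | 80.5% | not applicable |
| 0.3 | 0.954 | 84% | about 80% |
| 0.5 | 0.866 | 91% | about 88% |
| 0.6 | 0.800 | 95% | about 93% |

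The simulated figures are lower because HC3 errors are slightly conservative at this size: type I error was 1.8% to 2.4% against 2.5%. At r = 0.3 that cost uses up the gain.

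For the pooled 46 v 46 comparisons, power at 12 mmHg is already about 98%, so the benefit there is a narrower interval. By the factor √(1 − r²), before any robust-error cost, the narrowing is 1 − 0.954 = 4.6%, 1 − 0.866 = 13.4% and 1 − 0.800 = 20.0%.

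**The case against.** The strongest answer is the repeated-measures sentence in 3.13. MAP is recorded every 5 minutes, so it plausibly falls under the general linear model, which works on means. A reader might infer that a Kolmogorov-Smirnov result will decide how MAP is tested and that the mean difference will never be estimated. The documents do not support that. No sentence says the check selects the test; it follows directly on the sentence about presenting means or medians, and may serve that purpose. The ANOVA wording may also be a word-order slip for the usual rule, with ranks for irregular data and ANOVA otherwise.

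A reader might also infer that baseline is ignored or that the sample size fails. Neither follows. Baseline enters the event definitions in 3.7 and could enter the general linear model as a time point, although the text does not say so. The 92 patients suffice without adjustment, which makes adjustment a gain in efficiency and not the repair of an error.

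All of this stands, and it limits the point. It does not remove it. The sized quantity reads as one summary per patient and reproduces as a two-group t-test, while the general linear model sentence promises corrected P values but no difference in mmHg and no interval. If the ANOVA wording is a slip, it still needs correcting, and the rule it was meant to state would itself choose the test from the data.

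**Conclusion.** The point holds as a gap in specification. The plan does not connect the 12 mmHg mean difference to one analysis, plans no confidence interval for any continuous outcome, and names no baseline covariate. It is worth changing but does not threaten the trial's size.

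If MAP is near normal, choosing between tests costs at most about 4 points of power at 23 v 23 (80.5% v 76.7%) and about half a point at 46 v 46. Inflated rejection under a pre-test switch (up to 6.9% at nominal 2.5%) arises only under the assumed skewed shape combined with unequal SDs.

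The larger benefits are an estimate in mmHg with its interval and, if the baseline correlation is 0.5 or more, better precision: power of about 88% to 93% against 80% at 23 v 23. At a correlation of about 0.3 the power gain is negligible. These figures rest on the plan's SDs and alpha of 0.025, and on correlations that the documents do not give.

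**What to change.** In 3.13:
- Name one MAP summary, for example each patient's mean intraoperative MAP, as the quantity sized in 3.6.
- Analyse it with one linear model containing baseline MAP, technique and monitoring, with heteroscedasticity-robust standard errors because the planning SDs differ. State when baseline MAP is taken.
- Report the adjusted mean difference in mmHg with its confidence interval. Set the interval's level to match the alpha the plan settles on, since 3.6 uses 0.025 and 3.13 uses 0.05.
- Use the same form for cerebral saturation and heart rate.
- State that the repeated-measures general linear model is supportive and describes the time course.
- Drop the Kolmogorov-Smirnov test as a selector of tests and correct the ANOVA wording.
- List in advance the outcomes to be analysed by ranks, such as pain score and lengths of stay.

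The cost is SAP wording only. No patients are added, and the baseline values are already needed for the 20% definitions. The downsides are a mean-based model for outcomes that may be mildly skewed, which the robust errors largely cover, and little gain in precision if the baseline correlation is near 0.3.

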2. OBJECTIVES

2.1. General:

Compare intraoperative hemodynamic changes (cardiac output, blood pressure, heart rate, oxygen saturation) and cerebral oxygenation using peripheral cerebral saturation monitoring and continuous hemodynamic measurement of cardiac output or standard hemodynamics monitoring between two anesthetic techniques for shoulder surgery: interscalene block with sedation versus interscalene block with general anesthesia.

2.2. Specifics:

- Compare changes in cerebral tissue saturation between groups;
- Assess delirium and behavioral changes;
- Verify the superiority of continuous hemodynamic non-invasive monitoring of cardiac output compared to standard hemodynamic monitoring (only heart rate and blood pressure);
- Verify the relationship between standard hemodynamic monitoring (only heart rate and blood pressure) and continuous hemodynamic monitoring of cardiac output plus heart rate and blood pressure and the use of vasopressors, blood transfusion, infused volume;
- Evaluate complications of the anesthetic blockade technique with sedation over the blockade technique and general anesthesia;
- Assess postoperative pain, length of stay post anesthetic recovery and length of hospital stay between groups;

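### Section 3.13 gives no model terms for the 2 x 2 design and does not say whether monitoring is compared within or across techniques

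*Combined protocol and SAP*

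**What the plan says.** Section 3.7 sets out four groups: general anesthesia or sedation, each with continuous or standard monitoring. Section 3.10 allocates patients to these four groups at random. The general objective in Section 2.1 is a comparison "between two anesthetic techniques for shoulder surgery: interscalene block with sedation versus interscalene block with general anesthesia". A specific objective in Section 2.2 adds the superiority of continuous monitoring.

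Section 3.6 sizes the trial on MAP: "a difference in mean total MAP between groups of 12 mmHg was used", "with standard deviation of the group with continuous monitoring of cardiac output of 10 mmHg and in the group standard monitoring of 15 mmHg", 80% power, and "alpha error of 0.025 by Bonferroni correction due to be divided into 4 groups, a total sample of 92 patients will be need". Allowing for losses, this becomes 100 patients, 25 per group. The section does not name the pair of groups to which the 12 mmHg refers.

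Section 3.13 gives the analysis in three statements: "Comparisons between general anesthesia + block and block + sedation will be performed, as well as comparisons between standard and continuous monitoring"; "Quantitative variables will be compared using the Mann-Whitney test or irregularly distributed Anova when appropriate"; and "Variables with repeated measurements will be analyzed by linear general multiple model (GLM) with Bonferroni correction for P values". On the significance level it says "P values will be considered statistically significant when less than 0.05", two-tailed. The only multivariable model with a rule for its covariates is a logistic regression, which is not a model for mean MAP.

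**The concern.** In a 2 x 2 design the other randomised factor is a known source of variation. A model with both factors removes it from the error; a test with one factor leaves it in. Mann-Whitney cannot carry a second factor, an interaction or a baseline value. ANOVA and the GLM can, but the plan does not say that they will.

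The monitoring comparison also has two possible meanings. It can be made within each technique (1A v 1B and 2A v 2B) or once across both. The two have different precision and answer different questions if the effect of monitoring depends on technique. With no contrast named, a reader cannot tell which effect the sample size serves, and the analyst could choose after seeing the data. The significance level adds to this: 0.025 in Section 3.6, but 0.05 in Section 3.13, where Bonferroni is mentioned only for the GLM.

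The technique comparison, which is the general objective, is affected too. The variation left in its error would be the plan's own 12 mmHg monitoring difference.

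**Working it through.** **Inputs from Section 3.6:** difference 12 mmHg; SD 10 (continuous) and 15 (standard); power 80%; alpha 0.025, taken as two-sided following Section 3.13; 92 patients, or 23 per group.

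**1. The plan's own figure.** For two groups of n, SE = sqrt((10² + 15²)/n) = sqrt(325/n). With the Welch t test (noncentral t), power is 0.780 at n = 22 and 0.801 at n = 23. Four times 23 is 92, an exact match. (The normal approximation gives 21.5, so 22 per group and 88.) The two SDs belong to the two monitoring types, so 92 fits continuous v standard within each technique. A single comparison across techniques with the same inputs would need 23 per monitoring arm, 46 in all.

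**2. What the level of the contrast changes (23 per group).**
- Within one technique: SE = sqrt(325/23) = 3.76 mmHg; power for 12 mmHg at 0.025 is 0.801.
- Across techniques, two-factor model: SE = sqrt(650/(4 x 23)) = 2.66 mmHg; power 0.986.
- Interaction (difference of differences): SE = sqrt(650/23) = 5.32 mmHg; power for 12 mmHg at 0.05 is about 0.61.

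**3. Technique test with monitoring left out.** Each technique group is half continuous and half standard. The within-group variance is (100 + 225)/2 = 162.5. Leaving in a 12 mmHg monitoring effect adds (12/2)² = 36, giving 198.5, and 198.5/162.5 = 1.22.

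A power formula that simply inserts 198.5 is somewhat pessimistic. In a balanced design the left-in effect enlarges the estimated error but not the actual variability of the technique difference. The figures below are therefore simulated, with exactly 23 per group and one-way ANOVA as the one-factor test.

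| Quantity | Alpha | One factor | Two factors |
|---|---|---|---|
| Type I error | 0.025 | 0.012 | 0.025 |
| Type I error | 0.05 | 0.030 | 0.05 (nominal) |
| Power, 12 mmHg (planned) | 0.025 | 0.975 | 0.986 |
| Power, 12 mmHg (planned) | 0.05 | 0.989 | 0.994 |
| Power, 8 mmHg (illustrative) | 0.025 | 0.685 | 0.765 |
| Power, 8 mmHg (illustrative) | 0.05 | 0.789 | 0.844 |

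Mann-Whitney is close to one-way ANOVA here (power 0.684 v 0.687 in one run for 8 mmHg at 0.025).

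**4. Monitoring test.** Within a technique the other factor is constant, so nothing is lost. Across techniques the loss depends on the technique effect. Section 3.6 cites MAP falls of about 30% and 5.6%, a gap of 24.4 percentage points. At an assumed starting MAP of 80-100 mmHg that is 19.5-24.4 mmHg. With 22 mmHg left in the error, power for a 12 mmHg monitoring effect falls from 0.987 to 0.930 at 0.025.

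**5. Baseline MAP.** Adjustment removes r² of the residual variance. The documents give no r. For an assumed 0.3-0.6, the saving is 0.3² to 0.6², or 9-36%.

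**The case against.** The strongest reply is that MAP is recorded every 5 minutes, so Section 3.13 sends it to the GLM, which can hold both factors, the interaction and a baseline value. This stands in part. The power losses above are conditional on a one-factor analysis of MAP, which the plan does not state. But the GLM's terms are not stated either, so nothing commits the analysis to the better form.

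Second, at the planned 12 mmHg the loss in the technique test is about 1 point or less. This stands. The 5-8 points arise only at 8 mmHg, a value that is not in the documents. If the technique effect is near the 20 mmHg implied by the cited falls, simulated power for technique is 1.00 either way.

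Third, if monitoring is compared within technique, as the arithmetic suggests, the monitoring loss disappears. This also stands.

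A reader might infer that the one-factor tests are biased or inflate false positives. They do not: the randomised groups are balanced, and the tests err on the conservative side. A reader might also infer that 92 is wrong, or that Section 3.6 commits the trial to within-technique contrasts. The number reproduces, and the pair of groups is simply not named.

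**Conclusion.** The point holds as a gap in specification that can be closed without more patients. Section 3.13 does not state the factors, the interaction, the baseline covariate or the level of the monitoring contrast, no other section supplies them, and the 0.025 of Section 3.6 is not carried over. It is not an invalid analysis or an underpowered trial.

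The cost of one-factor tests, if they were used for MAP, is conservatism plus about 1 point of power or less at 12 mmHg and 5-8 points at 8 mmHg. An across-technique monitoring test would lose about 6 points at 12 mmHg if the technique effect is 22 mmHg. These figures assume the plan's SDs, 23 per group and no interaction; the 8 and 22 mmHg effects and the baseline correlation are assumptions. The more important consequence is that the effect the trial was sized for cannot be identified from the text. The change should be made.

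**What to change.** Amend Section 3.13 as follows.

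- **Mean intraoperative MAP:** a linear model with technique, monitoring, technique x monitoring and baseline MAP, with standard errors that allow unequal variances (the plan itself assumes SDs of 10 and 15). The baseline can be the initial MAP that Section 3.7 already uses to define hypotension, with its time point fixed.
- **The 5-minute series:** list the same terms plus time in the repeated-measures model.
- **Reporting:** both main effects, the monitoring effect within each technique and the interaction, all with confidence intervals. State that the interaction test has limited power (about 0.61 for 12 mmHg at 0.05).
- **Confirmatory contrasts and alpha:** name them and carry 0.025 over from Section 3.6. One choice is both main effects at 0.025 each, with power about 0.986 for 12 mmHg at 92 patients. If technique and the two within-technique monitoring contrasts are all confirmatory, each is tested at 0.05/3 = 0.0167. Power per within-technique contrast is then 0.751 at 23 per group and 0.794 at 25, so the power statement would need revising.
- **Source of MAP:** Section 3.7 has standard-monitoring patients wear a blinded ClearSight as well as having cuff pressures. State which supplies the analysed MAP, and use the same device in all four groups where the blinded pressures are recorded. The documents do not say whether they are, so this may need a change to data capture.

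Apart from that, the cost is SAP wording in the same software, a few degrees of freedom, and a baseline time point to fix in advance. With both main effects as the confirmatory pair, no more patients are needed.

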The beach chair position was suggested in 1988 by Skybar to avoid complications from the lateral decubitus position. The patient is set up in a sitting position with at least 60°, the patient's shoulder is brought slightly off the table with a sheet under the scapula (3). This position makes it possible to prevent neurological complications, such as neuropathies of the brachial plexus, peroneal nerve, axillary and musculocutaneous nerve, and facilitates the visualization of structures. In addition to these advantages, a more anatomical position can also be inferred, facilitates the examination under anesthesia, hanging arm does not hinder the visualization of the anterior portals, does not need repositioning for conversion to open surgery, can be performed only with regional anesthesia, arm mobility during the surgery. There are some disadvantages, such as increased risk of hypotension and bradycardia with cardiovascular and neurological complications, dark band in the visualization of the subacromial space, fluid under the camera making visualization difficult, increased risk of air embolism and expensive surgical table equipment (3);(4);(6). The beach semi-deck position is a position that reduces the chair angle to 30° to try to reduce hemodynamic complications (7). These changes can be enhanced by the anesthetic technique used, such as general anesthesia, especially in elderly and hypertensive patients, and when controlled hypotension methods are used for better visualization of the surgical field (8). No technique is totally risk free; however, the most used technique today is the beach chair position. There are several hemodynamic monitoring techniques for intraoperative evaluation, such as invasive and non-invasive monitoring. Non-invasive hemodynamic monitoring can be the standard (heart rate and blood pressure) or continuous monitoring of cardiac output plus heart rate and blood pressure. In addition, there is also monitoring of cerebral oxygenation continuously. The use of continuous monitoring of cardiac output and monitoring of cerebral oxygenation can minimize complications in patients undergoing surgery in a beach chair position through early detection of cerebral hypoperfusion and hypotension, thus, complications are early reversed (9);(10);(11);(12);(13).

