3.4. Inclusion criteria

- Patients of both genders, over 18 years of age;
- Patients undergoing arthroscopic shoulder surgery in a beach chair position.

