3.10. Data collect

After receiving an explanation about the procedures to be performed and signing the consent form, patients will be allocated into 4 groups as explained above using a table of random numbers. Data collected will be age, weight, height, race, gender, ASA, comorbidities, medications in use. During the surgical procedure, the analyzed data will be medications, infusion volume, blood components, vasopressor, anesthetic and surgical complications, anesthesia and surgery time.

In addition, systolic, diastolic and mean blood pressure, heart rate, cerebral O₂ saturation, peripheral O₂ saturation, axillary temperature, BIS value, cardiac index (in patients who will use clear sight) and et CO₂ (in patients who will be intubated) every 5 min intraoperatively and during post-anesthetic recovery (PAR) (27).

Postoperatively, the data analyzed will be: anesthetic recovery time, hospital stay, need to be referred to the intensive care unit (ICU), length of stay in the ICU and if the patient died. In addition, the visual numerical pain scale and the descriptive verbal pain scale will also be evaluated in the PVR and 24 hours after the procedure (28).

Sedation assessment will be performed using the intraoperative RASS scale for patients who are allocated to the sedation + interscalene brachial plexus block group and postoperatively for all groups. The values of the RASS scale are shown in table 1. The Confusion Management Method in the ICU (CAM-ICU) scale will be used to assess delirium, the table with the parameters used will be shown in figure 5 (29);(30).

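### The continuous MAP, cardiac-index and rScO₂ comparisons name no baseline covariate, although age and hypertension status are already recorded: a modest, cheap gain in precision is left unused

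*Combined protocol and SAP*

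**What the plan says.** Section 3.13 sets out the two comparisons of interest: "Comparisons between general anesthesia + block and block + sedation will be performed, as well as comparisons between standard and continuous monitoring". Quantitative variables go to Mann-Whitney or ANOVA, and repeated measurements to a general linear model with Bonferroni correction. No covariate is named for either. The only multivariable model is a multiple logistic regression reported as odds ratios. Its response is not named, and its explanatory variables are chosen by bivariate P value or clinical relevance.

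The Introduction says that the anesthetic technique, general anesthesia for example, can amplify the hemodynamic changes of the beach-chair position, "especially in elderly and hypertensive patients". Section 3.4 admits "Patients of both genders, over 18 years of age", and Section 3.5 excludes on neither age nor hypertension. Section 3.10 states: "Data collected will be age, weight, height, race, gender, ASA, comorbidities, medications in use". Section 3.12 randomizes in blocks of 8 and gives no stratification factor. Section 3.7 defines hypotension and reduced rScO₂ partly by a fall from an initial or baseline value, so a starting value for these two outcomes is foreseen.

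Section 3.6 sizes the trial on MAP: "a difference in mean total MAP between groups of 12 mmHg was used", with "considering the study power of 80% and alpha error of 0.025 by Bonferroni correction due to be divided into 4 groups" and "standard deviation of the group with continuous monitoring of cardiac output of 10 mmHg and in the group standard monitoring of 15 mmHg".

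**The concern.** The plan singles out two patient characteristics as relevant to its outcomes, admits a population in which both will vary, and records both. It then gives them no stated role in the continuous comparisons. Neither the randomization nor the analysis balances or accounts for them.

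Three things are at stake. First, any outcome variance that these variables explain stays in the error term and widens the intervals. Second, groups of 25 or 50 can differ by chance in age or hypertension, and readers will ask whether this matters. Third, if covariates are brought in only after the data are seen, the choice is open to discretion. A short list fixed in advance deals with all three.

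**Working it through.** **Inputs.** From Section 3.6: difference 12 mmHg; SD 10 (continuous monitoring) and 15 (standard monitoring); alpha 0.025; power 80%; 92 patients before losses, 100 after, 25 per group. From Section 3.13: two-sided tests. Assumed, because the documents give no figure: the share of outcome variance explained by the covariates (R²) is 5%, 10% or 20%; 40% of patients are hypertensive.

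**The plan's own figure.** The unadjusted standard error (SE) with n per arm is sqrt(10²/n + 15²/n) = sqrt(325/n). At n = 23 this is sqrt(14.13) = 3.76 mmHg. The noncentral t with Welch degrees of freedom (about 38) gives power 80.1% at 23 per arm and 78.0% at 22. So 23 per group is the minimum, and 4 x 23 = 92 matches "a total sample of 92 patients will be need". No covariate adjustment is needed to reach it.

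**The comparisons in Section 3.13.** These are pooled over the other factor, so 92 patients give 46 vs 46: SE = sqrt(325/46) = 2.66 mmHg. The same SE holds for technique if monitoring is in the model, since each technique arm then has average variance (100 + 225)/2 = 162.5, and 2 x 162.5/46 = 325/46. Unadjusted power for 12 mmHg is already 98.6%.

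**Gain and price of adjustment.** Adjustment multiplies the variance by (1 − R²). Estimating two covariates under chance imbalance multiplies it by about 1 + 2/(N − 5):
- N = 92: 1 + 2/87 = 1.023, a cost of about 2%.
- N = 46: 1 + 2/41 = 1.049, a cost of about 5%.

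Net SE = SE x sqrt[(1 − R²)(1 + 2/(N − 5))]. Power is the noncentral t with two degrees of freedom removed.

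| Assumed R² | SE, 46 vs 46 (mmHg) | SE, 23 vs 23 (mmHg) | Power, 23 vs 23 |
|---|---|---|---|
| None (unadjusted) | 2.66 | 3.76 | 80% |
| 5% | 2.66 x 0.986 = 2.62 | 3.76 x 0.998 = 3.75 | 80% |
| 10% | 2.66 x 0.960 = 2.55 | 3.76 x 0.972 = 3.65 | 82% |
| 20% | 2.66 x 0.905 = 2.40 | 3.76 x 0.916 = 3.44 | 87% |

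Break-even, where gain equals price, is R² = 2/(N − 3): about 2% for the pooled comparisons (2/89) and about 5% for 23 vs 23 (2/43).

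**A third covariate.** If the pre-anesthesia value is added, the price becomes about 3/(N − 6): 3/86 = 3.5% pooled and 3/40 = 7.5% at 23 vs 23. The R² that counts is then that of all three together.

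**Chance imbalance.** The SD of the difference in the share of hypertensive patients is sqrt(2 x 0.4 x 0.6/n): 0.139, or 14 percentage points, for 25 vs 25, and 0.098, or 10 points, for 50 vs 50.

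**The case against.** The strongest reply is that nothing here is broken. Randomization makes the unadjusted comparisons valid, the sample size reproduces without adjustment, and the pooled MAP comparisons have ample power for 12 mmHg. All of this stands. A reader might infer that omitting age and hypertension biases the results or undermines the 80% power; the documents support neither.

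Second, the Introduction's sentence is about the anesthetic technique: age and hypertension mark where its effect is larger. That points to effect modification at least as much as to prognosis, and the sentence names neither cardiac index nor rScO₂. This also stands. It would be too strong to say that the sponsor has declared both variables prognostic for all three outcomes. Additive covariates sharpen the average difference; they do not test whether it varies with age or hypertension.

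Third, adjustment is not free, and its benefit rests on an assumed R². That stands too. At 5% the gain at 23 vs 23 vanishes. If the baseline outcome is in the model, age and hypertension may add little beyond it, and the documents give no figure to settle this.

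Fourth, Section 3.13 can be said to cover the matter in part: the logistic regression may admit clinically relevant variables, and a GLM can take covariates. This carries less weight. Logistic regression yields odds ratios for binary responses, selects its variables partly from the data, and does not adjust a MAP, cardiac-index or rScO₂ difference. That a GLM could take covariates does not say which ones it will take.

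**Conclusion.** The point holds as a modest efficiency improvement. Section 3.13 names no baseline covariate for the continuous comparisons, although suitable ones are already collected, and a linear model with fixed covariates would be the better choice. With Section 3.6's SDs and an assumed R² of 5% to 20%, the net reduction in the pooled SE is about 1% to 10% (2.66 to between 2.62 and 2.40 mmHg). At 23 vs 23 the net effect on power runs from nil to about 7 percentage points.

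For MAP in the pooled comparisons the benefit is a narrower interval, since power for 12 mmHg is already 98.6%. It may matter more for cardiac index and rScO₂, for which Section 3.6 shows no power, but its size there cannot be derived from the documents. All of this depends on the assumed R². Protection against questions about chance imbalance, and against choosing covariates after the fact, does not depend on it.

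**What to change.** In Section 3.13, state that the technique and monitoring differences in MAP, cardiac index and rScO₂ will be estimated from a linear repeated-measures model. Its fixed covariates would be age (continuous), hypertension (yes/no, derived from the comorbidities and medications already recorded) and the pre-anesthesia value of the outcome where it is recorded. Name them now, keep them whatever their P values, and report the unadjusted difference alongside.

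Cost: one or two sentences and no extra patients. The analysis spends two or three degrees of freedom. The variance price for age and hypertension is about 2% in the pooled comparisons and 5% at 23 vs 23, and somewhat more with the baseline value added. The baseline fields must be complete for every patient, and hypertension needs a short written definition so that it is coded in the same way at all three hospitals.
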